## **2. STUDY OBJECTIVES**

### **2.1. Objectives**

#### **Primary Objective:**

To explore the pathological complete response (pCR) of lorlatinib as neoadjuvant treatment.

#### **Secondary Objectives:**

To explore the major pathologic response (MPR) assessed by investigator ; objective response rate (ORR) per RECIST 1.1 , investigator-assessed ; surgical outcomes ; Safety and tolerability.

### **Exploratory Objectives:**

Correlation between biomarkers with response and outcomes

## **2.2. Endpoints**

### **Primary Endpoint:**

- Pathological complete response (pCR), INV;

### **Secondary Efficacy Endpoints:**

[figure not shown]
- Major pathologic response (MPR) assessed by investigator (defined as no more than 10% residual viable tumor cells in the surgical specimen).
- Objective response rate (ORR) per RECIST 1.1 , investigator-assessed;
- Surgical outcomes and intraoperative events
- Rate of lymph node downstaging;
- Unanticipated delays to surgery;
- Surgical complication rate;
- Safety and tolerability per NCI-CTCAE v5.0.

### **Exploratory endpoints :**

- Correlation between biomarkers with response and outcomes

## **3. STUDY DESIGN**

### **Figure 1. Study Design**

### 3.1 Study design

This protocol delineates a Phase II, open-label, single-arm, prospective, multi-center study designed to evaluate the efficacy and safety of lorlatinib as a neoadjuvant therapy in patients with resectable ALK-positive non-small cell lung cancer (NSCLC). [Figure 1]

Eligible participants include male and female subjects aged  $\geq 18$  years, diagnosed with clinical stage IB, II, IIIA, or selected IIIB (including T4N2, as per the American Joint Committee on Cancer [AJCC] 8th edition) NSCLC, as assessed by positron emission tomography/computed tomography (PET/CT), or through computed tomography (CT), abdominal ultrasound, cranial MRI/CT, and bone scintigraphy. Enrollment criteria mandate that all tumors must test positive for ALK rearrangement, verified through Ventana ALK (D5F3), next-generation sequencing (NGS), etc. testing methods. All tumors will be of histo- and/or cytopathology consistent with NSCLC. Performance status (ECOG) 0-1 at enrolment, with no deterioration over the previous 2 weeks prior to baseline or day of first dosing of lorlatinib.

Upon meeting eligibility criteria, patients will be registered to receive oral lorlatinib at a dose of 100mg once daily (qd) for a period of 6-8 weeks, assessment will be conducted after 4 weeks, as determined by the attending clinicians based on the best clinical

practice. The duration of neoadjuvant therapy has been designed to optimize treatment efficacy while ensuring the feasibility of subsequent surgical resection.

Lorlatinib will be administered orally QD at approximately the same time of the day on a continuous daily dosing schedule, ie, without a break in dosing in the absence of drug-related toxicity. Patients must swallow the study medication whole and must not manipulate or chew the medication prior to swallowing. Patients should be instructed to take their medication at approximately the same time every day. A dosing card will be provided to the patients to provide guidance for the correct use of lorlatinib. Patients must be instructed that should they miss a dose or vomit any time after taking a dose, they must not “make it up” with an extra dose. Instead, resume the subsequent doses as originally prescribed. Any missed dose may be taken up to 6 hours prior to the next scheduled dose, otherwise it should be skipped and dosing resumed with subsequent doses as prescribed. The patient must be instructed to record all doses (including missed or vomited) in a dosing diary supplied by the site. If doses are missed or vomited, this must be indicated in the source documents and Case Record Forms (CRFs).

The response to neoadjuvant therapy will be evaluated by the investigators utilizing RECIST 1.1 criteria. Patients demonstrating no progressive disease as per these criteria will proceed to surgical resection with radical intent, scheduled within 6 weeks following the conclusion of lorlatinib neoadjuvant therapy. Patients completing the surgical intervention and pathological evaluation will conclude their participation in this study within 1-month post-surgery and may continue to receive subsequent treatment as deemed appropriate by their healthcare providers, based on prevailing clinical practice.

This study will intermittently collect blood specimens from patients at baseline, during neoadjuvant therapy, and perioperatively to explore changes in tumor biomarkers. Baseline and postoperative tissue specimens will be obtained, and Whole Exome Sequencing (WES) will be performed to investigate the correlation between neoadjuvant therapy efficacy and tissue mutation changes. Additionally, tissue

mutation results will be used to customize a blood testing panel to enhance detection rates.

Informed consent will be obtained from all participants prior to study enrollment. The consent process will ensure that patients are fully aware of the study's nature, its objectives, the investigational therapy involved, and the potential risks and benefits of participation. The study emphasizes rigorous adherence to ethical standards and patient safety, with a comprehensive plan in place for monitoring adverse events and implementing dose adjustments as necessary to manage toxicity.

Subjects will be on therapy until complete surgery and pathological evaluation, withdrawal of consent, death, or investigator decision dictated by protocol compliance, whichever occurs first. At the time of termination of study treatment, the patients could continue to receive treatment according to clinicians' decision in their clinical practice.

This study will take 18 months to enroll subjects, and each subject will be followed up for efficacy and safety during neoadjuvant process and 1-month post-surgery. Dose reduction information for management of AEs is included in Section 5.

Safety and efficacy assessments were performed throughout the treatment period and at the end-of-study visit. Routine safety assessments included the collection and evaluation of AEs, concomitant medications, vital signs, and body weight. Particular attention was given to AEs consistent with the lorlatinib toxicity profile (including lipid elevation, cognitive and mood disorder, etc.). Additional safety assessments performed at selected visits included ECOG PS, clinical laboratory tests, ECGs.

Safety assessments and efficacy assessments will be performed throughout the study as described in the Schedule of Activities (Table 1).

Study Activity	Screening & baseline ≤28 days of start of treatment	Cycle 1 Week 1-4	Cycle 2 Week 5-8	End of neoadjuvant (pre-surgery assessment)	End of treatment visit (Surgery complete)	Final follow-up visit (1 month after surgery)
Visits		Day 1	Day -4±2 day			
Informed consent 	X					
Medical history and demographics 	X					
ALK+ status	X					
Physical examination	X					
ECOG PS 	X	X	X	X	X	X
Brain scan MRI or CT 	X					
Vital signs  , Body weight, Height 	X	X	X	X	X	X
ECG 	X	X	X	X		X
Laboratory 						
Hematology 	X	X	X	X	X	X
Blood chemistry 	X	X	X	X	X	X
Urinalysis 	X	X	X	X	X	X
Pregnancy test 	X				(X)	
HBV, HCV, and HIV testing	X					
Prior/Concomitant medications 	X	X	X	X	X	X
Adverse events 	X	X	X	X	X	X
Tumor imaging assessments 	X	X		X	X 	X 
Subject status follow-up 	X	X	X	X	X	X
Lorlatinib dosing 		X-----X				
Tumor tissue sample 	X				X	
Blood sample 	X	X (2 weeks, 4 weeks,)	X (End of treatment)	X	X (3 days after surgery)	X

Abbreviations: CT, Computed Tomography; ECG, Electrocardiogram; ECOG, Eastern Cooperative Oncology Group; EGFR, epidermal growth factor receptor; MRI, magnetic resonance imaging; NGS, next-generation sequencing; PS, Performance Status.

1. Written informed consent is required within 28 days of start of treatment, and prior to any study specific screening procedures.

2. Medical History and demographics: General medical history including details of any concurrent illness, oncology history (including smoking status and history of weight loss in last 6 months) to be done at baseline.
3. Performance status will be assessed by the ECOG scale.
4. MRI is recommended as the preferred option.. Central nervous system (CNS) masses or meningeal involvement must be asymptomatic .and without the need for increasing doses of corticosteroids to manage CNS symptoms within two weeks of starting lorlatinib.
5. Vital signs include pulse rate, sitting or supine blood pressure, respiratory rate and body temperature. The information will be recorded in the subject's medical records and if clinically significant, data will be recorded as an adverse event (AE) in the case report form (CRF). Height will be measured at screening only.
6. ECG: A 12-lead ECG will be performed at screening and baseline for all subjects. If any subject experiences a cardiac or neurologic AE (e.g., syncope, dizziness, seizures, or stroke), unplanned ECG should be obtained at the time of the event. The ECG should be repeated if there is a clinical finding that indicates a need for a repeat ECG or if there is a finding of QTc >500 msec, and abnormal QTc findings confirmed by a manual reading by investigator or designee.
7. Laboratory studies will be performed locally (described as follows in footnotes 8-11) and may be performed up to 72 hours prior to scheduled visits to allow for availability of results at time of subject's scheduled clinic visit.
8. Hematology includes: hemoglobin, platelet count, white blood cell count, absolute neutrophil count, absolute lymphocyte count and absolute monocyte count.
9. Blood chemistry includes at screening: creatinine (and creatinine clearance to be determined by Cockcroft-Gault formula or standard formula for site), alanine aminotransferase (ALT), aspartate aminotransferase (AST), total bilirubin, serum total amylase and serum total lipase. Blood chemistry at subsequent visits includes: blood urea nitrogen or urea, sodium, potassium, magnesium, calcium, alkaline phosphatase, albumin, AST, ALT, total bilirubin, and creatinine, serum total amylase and serum total lipase should be assessed if deemed necessary by the investigator.
10. Urinalysis includes: protein, glucose, blood, urinary sediment. A dipstick urinalysis may be used; however if any abnormal findings are noted then a microscopic examination must be performed. If urine protein by dipstick is  $\geq 3+$ , then a urine protein/creatinine ratio (UPC) should be obtained. The patient may enter only if UPC is  $<2.0$ .
11. A pregnancy test for women of child-bearing potential should be done at screening and baseline. Pregnancy test result need to be known to be negative prior to study treatment. For baseline, in case of serum sample, pregnancy test needs to be conducted within 72 hours prior to Cycle 1 Day 1. In case of urine sample, pregnancy test needs to be conducted on Cycle 1 Day 1 before study treatment is started. It should be repeated at end of treatment visit, and as often as necessary, if mandated by institutional policy or at the discretion of the investigator.
12. Subjects will be enrolled only if they are able to stop (by discontinuation, substitution, or modification) medications that are prohibited, or if the metabolism is highly CYP2D6 dependent. Prior/concomitant medications shall be recorded at screening, and continuously throughout the study period up to the Post-Treatment Follow-Up Visit or until the subject begins a new anticancer therapy, whichever occurs first.
13. Adverse event assessment includes tumor-related, treatment-related and unrelated signs and symptoms. The reporting period for non-serious AEs starts from the time the subject has taken the first dose of study treatment and ends at last subject visit or upon initiation of a subsequent anticancer treatment, whichever occurs first. The reporting period for serious AEs starts once a subject provides informed consent and ends 28 days after the last dose of study treatment irrespective of the start of

any subsequent anticancer treatment. Subjects must be followed for AEs at Post-Treatment Follow-up Visit at least 28 (and no more than 35) days after the end of treatment, or until all drug-related toxicities have resolved or are deemed irreversible, whichever is later. The National Cancer Institute Common Terminology Criteria for Adverse Events, Version 5.0 (CTCAE v5.0) will be used to grade AE severity.

14. Tumor assessments will include: PET/CT, or through computed tomography (CT), abdominal ultrasound, cranial MRI/CT, and bone scintigraphy at screening, in order to determine the accurate TNM staging. Physical examination for peripheral adenopathy or skin/subcutaneous nodules representing target measurable (by caliper) disease, if any are present.. Imaging serves also as safety assessment to monitor/exclude pulmonary toxicity. Chest X-ray will be performed on the first postoperative day to assess the surgical outcome and any procedural events. A chest X-ray will be conducted one month postoperatively to evaluate postoperative pulmonary recovery, including the presence of pleural effusion.
15. Subject Status Follow-up for Survival: Repeat tumor assessments are suggested to be done approximately every 4 weeks from the date of CT/MRI at the end of study treatment. Telephone contact approximately every cycle from post treatment follow-up visit to obtain regular follow-up is recommended. The information collected for subsequent therapies should include enumeration of the post-study treatment, including drugs administered, and date of initiation and discontinuation of each drug; and will be recorded in the CRF.
16. Lorlatinib 100 mg, once daily, will be administered to subjects starting on Cycle 1, Day 1. Subjects should be instructed to take their medication at approximately the same time every day. The tablets will be taken with at least 6 ounces (180 ml) of water with or without food. Treatment compliance check: The site must follow up with each subject on the day of each cycle's visit to confirm that the subject understands and complies with the dosing instructions for lorlatinib.
17. For patients meeting the inclusion criteria, tissue samples will be collected in the form of formalin-fixed paraffin-embedded blocks, formalin-fixed tissue, or fresh tissue at baseline and postoperatively. Details regarding specimen handling, storage, and residual sample management can be found in the laboratory manual.
18. For patients meeting the inclusion criteria, blood samples (20 mL each) will be collected at baseline, 2 weeks, 4 weeks, completion of neoadjuvant therapy, preoperatively, 3 days postoperatively, and 1 month postoperatively. Details regarding specimen handling, storage, and residual sample management can be found in the laboratory manual.

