## 6.2 Screening

All screening assessments are to be performed within 28 days prior to first study drug administration of lorlatinib. Assessment conducted prior to informed consent and within 28 days of first dose (Cycle 1 Day 1) can be used as data for screening. To establish subject eligibility for subsequent treatment, the following assessments will be completed:

- Confirm evidence of newly diagnosed stage IB, II, IIIA or selected IIIB (including T4N2, per AJCC 8th edition) resectable non-squamous NSCLC, allowable methods of disease measurement is PET/CT. The decision on which area of the body to be imaged is as determined by investigator judgment.
- Confirmation of ALK rearrangement via Ventana D5F3, NGS, etc. testing methods by local laboratory. Ventana D5F3 is recommended for reconfirmation in NGS and other testing methods;
- Vital signs, body weight and height will be measured (see Section 7.3.3);
- ECOG PS (see [Appendix 1](#));
- Blood and urine samples will be collected (hematology, blood chemistry, coagulation, pregnancy test (female subjects with reproductive potential), urinalysis; see Section 7.3.2);
- A 12-Lead ECG reading will be performed with attention to QTc interval, with Fridericia's or Bazett's correction for abnormal heart rate as applicable (see Section 7.3.1);
- Prior/concomitant medication and SAE data will be collected. This would include the drug name, start/stop dates and indication.

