### 6.3 Baseline

The following text outlines baseline assessments and procedures to be performed (see Schedule of Activities **Table 1**).

Within 2 weeks prior to Cycle 1 Day 1, the following assessments will be performed. It is unnecessary to repeat assessment at baseline if screening assessment and all laboratory evaluation items for baseline were performed at screening and within 2 weeks prior to Cycle 1 Day 1 (Pregnancy test result need to be known to be negative prior to study treatment: In case of serum sample, pregnancy test needs to be conducted within 72 hours prior to Cycle 1 Day 1. In case of urine sample, pregnancy test needs to be conducted on Cycle 1 Day 1 before study treatment is started.) and there is no clinical reason to believe the baseline has significantly changed:

- Vital signs and body weight will be measured (see Section 7.3.3);
- Demographics and medical history (relevant clinical events and conditions including tumor-related signs and symptoms); collection of subject reported weight loss over the past 6 months; history of smoking;
- Physical examination will be performed;
- A 12-Lead ECG reading will be done. QTc must be less than CTCAE v5.0 Grade 2 ( $\leq 480$  msec) using Fridericia's or Bazett's correction formula with a manual reading by the investigator if required. The ECG may be repeated for evaluation of eligibility after management of correctable causes for observed QTc prolongation (see [Section 7.3.1](#)). Subject whose heart rate  $<45$  beats per minute in the presence of clinical symptoms (e.g., hypotension, evidence of hypoperfusion) will not start study treatment;
- Blood samples will be collected (hematology, blood chemistry, coagulation and pregnancy test; see Section 7.3.2;
  - a. Estimated creatinine clearance  $\geq 30$  mL/min (as determined by Cockcroft-Gault formula or the study site's standard formula);
  - b. Absolute neutrophil count (ANC)  $\geq 1500$  cells/mm^3;
  - c. Platelets  $\geq 100,000$  cells/mm^3;
  - d. Hemoglobin  $\geq 9.0$  g/dL;
  - e. Bilirubin  $\leq 1.5 \times$  ULN;
  - f. AST (also known as SGOT) and ALT (also known as SGPT)  $\leq 2.5 \times$  ULN ( $\leq 5.0 \times$  ULN if hepatic metastases);
- Prior/concomitant medication and SAE data will be collected and reviewed;

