### **6.4.2 Cycle 1 Day 15 ( $\pm 2$ days)**

Subjects will attend the clinic on Cycle 1 Day 15 ( $\pm 2$  days) for the following assessments:

- Vital signs and body weight will be measured (see Section 7.3.3);
- Concomitant medication and AE data will be collected and reviewed.

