### **6.4.3 Day 1 of Subsequent Cycles (-4/+2 days)**

Subjects will visit the investigator site on Day 1 (-4/+2 days) of each subsequent cycle for the following assessments:

- Vital signs and body weight will be measured (see Section 7.3.3);
- ECOG PS (see [Appendix 1](#));
- Blood samples will be collected (hematology, blood chemistry, see Section 7.3.3). Safety laboratory tests may be done up to 72 hours prior to the visit;
- Concomitant medication and AE data will be collected and reviewed;

After the end of Cycle 1, follow the study schedule as outlined in Table 1:

- Tumor assessments will occur after the end of Cycle 1 then follow the study schedule as outlined in Table 1. The assessment may be performed up to 7 days prior to the visit to facilitate availability of results to the investigator at the time of the clinic visit.

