**Table 5: Laboratory Evaluations**

Screening for Eligibility		
Hematology	Blood Chemistry	Other
Hemoglobin	AST (SGOT)	Urinalysis (blood, protein, glucose, by dipstick; microscopic examination of sediment if abnormalities on urine dipstick)
Platelet count	ALT (SGPT)	
WBC count	Creatinine	
Absolute neutrophil count	Total bilirubin	Calculation of the creatinine clearance determined by the Cockcroft-Gault formula or site's standard formula.
Absolute lymphocyte count		
Absolute monocyte count		Pregnancy Test (urine or serum)

Baseline and during the Treatment Period		
Hematology	Blood Chemistry	Other
Hemoglobin	Alkaline phosphatase	Pregnancy test (urine or serum) at baseline.
Platelet count	AST, ALT	In case of serum sample, pregnancy test needs to be conducted within 72 hours prior to Cycle 1 Day 1. In case of urine sample, pregnancy test needs to be conducted on Cycle 1 Day 1 before study treatment is started. Pregnancy test (urine or serum) at end of treatment if mandated by institutional policy or at the discretion of the investigator.
WBC count	Total bilirubin	
Absolute neutrophil count	Calcium (total or ionized)	
Absolute lymphocyte count	Magnesium	
Absolute monocyte count	Potassium	
	Sodium	
	BUN or urea	
	Albumin	

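### The protocol recommends statin and lorlatinib steps by cholesterol and triglyceride grade, but its laboratory lists and visit sections name no lipid test

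*Protocol*

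**What the plan says.** **The guidance that needs lipid grades.** Section 5.3 suggests starting a statin at a Grade 1 rise in either lipid and raising the dose if control is inadequate. It warns that, without a statin, levels can reach Grade 3 by the following cycle. Table 3 has a cholesterol row and a triglycerides row, each with an entry for Grades 1 to 4. At Grade 4 lorlatinib is withheld until Grade 2 or lower, then reduced or rechallenged. Section 3.1 singles out lipid elevation among the adverse events to watch.

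**The tests that are scheduled.** Table 1 has a blood chemistry row and no lipid row. Footnote 7 refers the reader to the notes that follow it: "Laboratory studies will be performed locally (described as follows in footnotes 8-11". Footnote 9 then gives two lists:

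- At screening: "Blood chemistry includes at screening: creatinine (and creatinine clearance to be determined by Cockcroft-Gault formula or standard formula for site", followed by ALT, AST, total bilirubin, amylase and lipase.
- Later: "Blood chemistry at subsequent visits includes: blood urea nitrogen or urea, sodium, potassium, magnesium, calcium, alkaline phosphatase, albumin, AST, ALT, total bilirubin, and creatinine", with amylase and lipase if the investigator thinks them necessary.

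Table 5 itemises chemistry to the level of "Calcium (total or ionized", again without lipids. The visit sections order chemistry as a block. Section 6.2 has "Blood and urine samples will be collected (hematology, blood chemistry, coagulation, pregnancy test (female subjects with reproductive potential), urinalysis", Section 6.3 has "Blood samples will be collected (hematology, blood chemistry, coagulation and pregnancy test" and Section 6.4.3 has "Blood samples will be collected (hematology, blood chemistry, see Section 7.3.3".

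**The concern.** A lipid rise without symptoms is found only by measuring it. If no lipid test is ordered, no grade exists and the recommended steps are never prompted. The protocol itself identifies this toxicity as common and quick to develop, and dosing lasts only 6 to 8 weeks.

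Two things are at stake. The first is patient safety, because early statin treatment depends on a result that the schedule does not ask for. The second is the descriptive safety endpoint. Section 9.3 reports the frequency, severity and timing of adverse events and laboratory abnormalities. If each of the six sites decides whether and when to test, lipid findings would partly reflect local habit. Without a pre-treatment value it would also be hard to tell a treatment-emergent rise from a pre-existing one. An analysis plan cannot repair this later, since it cannot supply values that were never collected.

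**Working it through.** The protocol states no figure to reproduce. The check is an inventory of where lipid values are needed against where they are ordered.

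**Needed.** Table 3: 2 lipids × 4 grades = 8 entries that require a cholesterol or triglyceride grade. Section 5.3 adds the Grade 1 statin advice.

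**Ordered.**

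| Place | Cholesterol, triglycerides or lipid panel named? |
|---|---|
| Table 1 rows | No |
| Footnote 9, screening list | No |
| Footnote 9, later visits | No |
| Table 5, screening | No |
| Table 5, baseline and treatment | No |
| Sections 6.2, 6.3, 6.4.5 | No; coagulation is added by name |
| Section 6.4.2 (Day 15) | No; no safety laboratory tests listed |
| Section 6.4.3 | No; its cross-reference leads to Vital Signs |
| Sections 6.4.1, 6.4.6 | No |

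So 0 of the 2 laboratory lists (footnote 9 and Table 5) and none of the visit sections name a lipid test. Footnote 9 is running text and agrees with Table 5, so a table broken in text extraction is an unlikely explanation. The laboratory manual is cited only for tissue and biomarker blood (footnotes 17 and 18), not for safety chemistry.

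**Timing of the draws a lipid test could join.** These figures describe when blood is taken. They do not measure the size of the omission.

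- Inputs: Cycle 1 is weeks 1 to 4 (Table 1), so Cycle 2 Day 1 is nominally Day 29. The course is 6 to 8 weeks, or 42 to 56 days. The visit window is −4/+2 days (Section 6.4.3), and laboratory tests may be done up to 72 hours before the visit (footnote 7, Section 6.4.3).
- Earliest Cycle 2 sample: 29 − 4 − 3 = Day 22, after 21 days; 21/56 = 37.5% of the course.
- Latest Cycle 2 sample: 29 + 2 = Day 31, after 30 days; 30/42 = 71.4%.
- Day 15 ± 2 days (Section 6.4.2), sample taken at the visit: 12 to 16 days elapsed; 12/56 = 21.4% to 16/42 = 38.1%.

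Once windows are applied to both, the two ranges just meet. An earlier look at Day 15 is useful, but the contrast is modest.

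**Cost.** Screening/baseline, Cycle 2 Day 1 and end of neoadjuvant therapy: 3 × 25 = 75 samples; 75 × 2 = 150 assays. If the trial stops after stage 1: 3 × 15 = 45 samples; 45 × 2 = 90 assays.

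**The case against.** The case on the other side has real substance.

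- **The steps are guidance.** Section 5.2 encourages local best supportive care or use of the guidance, Table 3 gives recommendations, and Section 5.3 is suggested management. This stands: the steps are not binding. They still cannot be followed without a lipid value.
- **Testing is plainly expected.** Section 5.2 promises close toxicity monitoring, Section 3.1 names lipid elevation, and the lists say what chemistry includes, which permits more. This also stands. A reader might infer that the protocol excludes lipid testing or that no site will do it, and the text supports neither. The gap is that no test is named or timed.
- **The lists are not exhaustive, and lipids are not the only gap.** Coagulation is ordered in three visit sections but is in neither list. Table 5 omits the amylase and lipase that footnote 9 names. Table 3's own note grades hyperuricemia and hypophosphatemia, while neither uric acid nor phosphate is listed. This rules out calling lipids a singular exception. It does not supply the missing test, and coagulation shows that extra tests were named where they were wanted.
- **The lipid steps do not need a baseline.** A reader might infer that Table 3 cannot operate without a pre-treatment lipid value. The legible lipid thresholds use Grade 2 or lower, whereas the general toxicity rows allow return to baseline. A pre-treatment value matters for interpreting adverse events, not for applying these rows.
- **Nothing requires a Day 15 test.** Section 5.3 speaks of cycles, which supports testing before treatment and at each cycle. This stands, so Day 15 is an option only.

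**Conclusion.** The point holds as an omission from the safety schedule that should be corrected. Following the protocol to the letter yields no lipid grade and no pre-treatment lipid value, for a toxicity that the protocol itself describes as the most frequent in an earlier phase 3 study and for which it recommends graded action. Lipid abnormalities under Section 9.3 could be under-reported and could differ by site.

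The size of any under-ascertainment cannot be given. It would need the expected lipid event rate and the sites' usual testing practice, and the protocol states neither. If every site tests lipids routinely the practical effect could be nil.

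It would be wrong to read this as a threat to the trial's main result. pCR is assessed on surgical specimens, and the Simon boundaries (1 or fewer of 15 to stop, 6 or more of 25 to reject) do not use laboratory data. The consequence is confined to patient safety and the descriptive safety summary.

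**What to change.** Add total cholesterol and triglycerides to both chemistry lists in footnote 9 and to both parts of Table 5, at three existing chemistry time points: screening/baseline (before the first dose), Cycle 2 Day 1 and end of neoadjuvant therapy. Counting screening/baseline as one sample, the cost is 75 samples and 150 routine assays for 25 patients, with no new visit and no new draw.

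Optionally, add a lipid test at Cycle 1 Day 15. Section 6.4.2 already brings patients in ("Subjects will attend the clinic on Cycle 1 Day 15"), and footnote 18 already provides a 2-week blood draw. This would need 25 extra tubes (25 × 2 = 50 further assays) and a line in Section 6.4.2, which at present lists only vital signs, weight, concomitant medication and adverse event review.
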